We plan to conduct a 2x2 *randomized, controlled, crossover trial* in persons with prediabetes (n = 40; 1:1 M/F) to assess 2-wk consumption of white bread (WB) vs whole wheat bread (WWB) on cardiometabolic and gut microbiome parameters (Figure 1). Participants will be recruited from the Columbus, OH area,

consistent with earlier successful studies conducted by the [name] lab. Participants will be block-randomized in 4-unit blocks to receive WB or WWB (128 g/day; 4 bread slices/d, according to the USDA “My Plate” recommendation and other similar studies)^{14, 53, 54} for 2-wks. During each study arm, participants will be provided standardized test meals containing WB or WWB, these foods will be prepared and packaged in the Human Nutrition Metabolic Research Kitchen (Evans Laboratory) to be devoid of whole grain products, probiotic-containing foods (e.g., yogurt), or fermented foods that are known to alter gut bacteria populations. Before and after each 2-wk study arm, a fasting blood sample will be obtained for metabolomic and clinical measures. Blood pressure and anthropometrics also will be assessed on days 1, 7, 14, and participants will collect a fecal sample to provide to the study team during their visits on day 1 and day 14. Lastly, on day 14, participants will simultaneously complete an oral glucose tolerance test and gut permeability test, which involves ingesting a glucose solution that also contains non-digestible sugar probes prior to collecting complete 24-hour urine samples for assessments of upper and lower gut permeability (described below). Upon completing these procedures, participants will undergo >2-weeks wash-out before repeating the study identically, but with crossover to the alternate bread diet.

B. Study Subjects

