Mixed effect modeling will be performed, diet and time will be included as fixed factors while participant serves as a random factor. False discovery rate (FDR) will be used to control type I error rate for microbiome and metabolome data, while the Bonferroni method will be applied for other measures (e.g., inflammatory markers). Data will be first normalized before analysis. Spearman correlations will be calculated to define associations between microbes, inflammatory genes, metabolites that show significant changes in highresponders.

To test whether the changes in microbes after WWB intake associate with the biological response, logistic regression will be fitted to each of the potential microbes or as a combination. We will also couple the logistic regression with receiver-operating characteristic (ROC) analysis to evaluate the specificity and sensitivity of the microbes that predict participants' biological response, and the area under the curve (AUC) of the microbial model will be displayed. Data analysis will be performed in R (open resource) or SAS (SAS, Inc; Cary, NC). The sample size was calculated in PASS 20 (NCSS, LLC; Kaysville, Utah).

C. Measurement/Instrumentation

All procedures will take place in the Human Nutrition Program located in Evans Laboratory. Infrastructure that is present includes a metabolic research kitchen, a private office to meet with participants, a clinical research laboratory for performing phlebotomy and research procedures, and a separate biochemical laboratory for processing and preserving biological specimens.

1. *Anthropometric Parameters and Blood Pressure.* At screening, day 1, 7, and 14, participants will rest for 15 minutes prior to determining blood pressure using an automated blood pressure cuff. BMI will be calculated from height determined from a wall-mounted stadiometer and weight from a calibrated scale.

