2. *Blood Chemistries.* Fasting plasma glucose and lipids (total cholesterol, HDL-C, triglyceride) will be measured by clinical assay (Pointe Scientific) at screening, day 1, and day 14. Fasting insulin will be measured by ELISA (ALPCO) at day 1 and day 14. Postprandial glucose (0-180 min at 30 min intervals) following an oral glucose tolerance test will also be measured on day 14. At the beginning and the end of each intervention arm, we will define the effects of WWB on inflammatory responses. We will assess intestinal inflammation by measuring fecal calprotectin and myeloperoxidase (i.e. indices of neutrophil inflammatory responses) by ELISA as we described.⁵² We will also measure systematic inflammatory responses in both fasting and postprandial serum by ELISA (CRP, IL-6 and -8, TNF α , MPO) and by RTPCR analysis of peripheral blood mononuclear cells (PMBCs; isolated at blood collection) to assess the expression of genes involved in TLR4/NF κ B signaling (TLR4, MyD88, p65, IL-6 and -8, TNF α , MPO, MCP-1).

3. *Endotoxin.* Serum endotoxin from the individual participant will be assessed on day 1 and day 14 using a high-sensitivity fluorometric assay (PyroGene rFC; Lonza) and endotoxin-free consumables as reported in our previous studies.⁵⁵ In our hands, inter- and intra-assay CV is 4.2-6.1%.

4. *Preparation of Whole Wheat Bread.* To ensure uniformity in WB and WWB test products throughout this controlled study, both types of breads to be used will be prepared by co-Investigator [name] (Department of Food Science and Technology) and provided to the [name] lab for clinical study. WWB and WB will be prepared in the [name] lab in the Parker Food Science and Technology Building as previously reported by Cong et al.,⁵⁶ using the modified AACC straight-dough bread-making method.⁵⁷ The formula, is 200 grams of flour, included 10.6 g yeast (active dry), 12.0 g sucrose, 3.0 g salt (NaCl), 6.0 g shortening, and 130.0 g of water. Ingredients will be mixed (KitchenAid, Benton Harbor, MI) until a sponge dough is formed, approximately 2.5 min. The dough will be placed into a 5-3/4" x 3-1/4" x

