8. MS-Metabolomics & Short Chain Fatty Acids. We will perform rigorous metabolomics analysis of serum samples on day 1 and day 14 and fecal samples provided at day 1 and day 14 from study participants use multiplex MS-based metabolomics with the following techniques: (1). Targeted LC-MS/MS metabolic profiling (TMP) methods using both regular and stable isotope-labeled chemical standards to achieve accurate, specific, and quantitative metabolite measurements of >200 metabolites from more than 25 metabolic pathways.⁷⁷ This method can provide accurate pathway-by-pathway measurement and validated metabolite identification for further biological system analysis, as demonstrated by our recent publications⁷⁸⁻⁸⁰. (2). We will also use a newly developed metabolomics approach, Globally Optimized Targeted (GOT)MS⁸¹ to analyze broader coverage of metabolites. GOT-MS combines many of the advantages of targeted detection and global profiling in metabolomics analysis, including the capability to detect unknowns, broad metabolite coverage, and excellent quantitation. (3) We will also use untargeted metabolomics for exploratory studies: Briefly, a Thermo LC-Q-Exactive Hybrid MS system will be used for untargeted analysis. Compound Discoverer 3.1 software will be used with customized workflows for different types of samples. Compound identification will be achieved by multiple database searches (HMDB, m/z cloud, METLIN, mass bank, etc.)⁸²⁻⁸⁴ and MS/MS fragmentation pattern comparisons to authentic standards. In addition, using our targeted LC-MS/MS-based panel of >50 frequently reported phytochemicals in whole wheat, such as representative alkylresorcinols, benzoxazinoids, phenolics (e.g., ferulic acid),^{4, 5} we will quantify these phytochemicals and metabolites in serum and fecal samples following enzymatic hydrolysis with β -glucuronidase/sulfatase.⁸⁵ Analyte identification and quantification will be confirmed by comparing fragmentation patterns relative to purified standards or reference databases. In addition to defining the effect of WWB treatment on host metabolism, time-dependent serum measures of alkylresorcinol concentrations of 19:0, 21:0, and 23:0 and total alkylresorcinols in study participants who consume WWB will objectively establish subject compliance to the dietary intervention.^{45, 86}

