If a participant is telephoned and is unavailable, a message will be left requesting a callback at a convenient time or that a member of the study team will try calling again at a later time. No confidential or sensitive information will be shared with third parties or left on answering machines.

3. Study timeline and activities occurring at each study visit. As indicated in **Figure 1**, each participant will complete a 2-arm (whole wheat bread; white bread), randomized, cross-over study. For this study, each participant will visit the study center a total of 13 times (screening visit plus 6 times per study arm), including:

- **Informed Consent & Screening Visit.** Potential participants will visit the study center to meet with a designated study team member. At this meeting, the informed consent will be reviewed with the potential participant and be allotted time to address any questions. If the participant agrees, the informed consent form will be signed for enrollment. If the participant is fasted, anthropometrics and blood pressure will be measured, and a fasting blood sample will be collected to determine whether circulating chemistries are within acceptable limits. If the participant is not fasted, these procedures will be scheduled at a time of mutual convenience. If the participant fulfills study inclusion criteria, the participant will proceed to complete Trial 1 procedures.
- **Trial 1 Procedures (2-week intervention to WWB or WB)**
 - *Day 1:* Participant will visit the study center for measures of anthropometrics and blood pressure, the collection of a fasting blood sample, and to pick-up daily meals for Days 13. All foods and beverages will be provided, and daily test meals will include WWB or WB. The participant will also provide a fecal sample that was self-collected within the preceding 24-hours.
 - *Day 3:* Participant will visit the study center briefly to pick-up meals that will be consumed on Days 4-6. Participant will return all uneaten foods and containers to the study team to determine actual food consumption during the preceding period.
 - *Day 7:* Participant will visit the study center briefly to pick-up meals that will be consumed on Days 7-10. Participant will return all uneaten foods and containers to the study team to determine actual food consumption during the preceding period. Measures of anthropometrics will be conducted and a urine sample will be collected to assess compliance to test meals.

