4. *Blood Collection and Sampling Handling.* Once at baseline (day 0; 14 mL), and at each time point of the postprandial trial (20 mL * 7 timepoints over 3-h), a blood sample will be collected into evacuated blood collection tubes. Collecting a total of 154 mL or 0.65 cups once during each study arm is necessary to ensure an adequate volume of plasma and serum for each time point to accurately analyze levels of glucose, insulin, endotoxin, and pro-inflammatory genes. During blood collection, participants may feel an initial pain when inserting the needle, bruising around the insertion area, lightheadedness, or fainting, which are common when donating blood. However, we do not foresee any additional significant risks for collecting this amount of blood over 3 hours, other than the risks stated previously.

Throughout the span of the study (~8-12 weeks in duration depending on participant/investigator availability) which consists of four weeks total of controlled feeding, a blood collection at day 0 and 14 and then repeated following a \geq 2-week washout period, and 1 screening day, we will be collecting a total of ~318 mL or ~1.34 cups) of blood. Urine will be collected in provided containers (VWR) containing 10% thymol to inhibit bacterial growth. We will then have the participants return their urine samples to the study center or coordinate with study personnel to meet at a public and mutual location to return their samples within 24-h after collection. Feces will be collected using a commercial commode specimen collection system (Fisher Scientific). Briefly, the collection kit consists of the necessary materials (e.g., gloves, waste bag) for participants to easily and hygienically collect their stool without contaminating the sample or themselves. Volumes of urine will be recorded and fecal mass and observations will be recorded based on the Bristol Stool Chart.⁸⁸

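### The mixed model leaves time undefined and omits period and baseline; if time is study day, its diet term is half the day-14 effect for secondary measures taken on days 1 and 14

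*Combined protocol and SAP*

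**What the plan says.** Section VI.B.3 (Power Calculation and Data Analysis) gives the whole model in one sentence: "diet and time will be included as fixed factors while participant serves as a random factor". The word time could mean three things in this design:

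- **Study day.** Section VI.A has "Before and after each 2-wk study arm, a fasting blood sample will be obtained for metabolomic and clinical measures". Section VI.C.2 has "Fasting insulin will be measured by ELISA (ALPCO) at day 1 and day 14", puts fasting glucose and lipids on the same days, and says of the inflammatory markers: "At the beginning and the end of each intervention arm, we will define the effects of WWB on inflammatory responses". Section VI.C.3 puts endotoxin on days 1 and 14. Section VI.C.8 takes metabolomics from "serum samples on day 1 and day 14 and fecal samples provided at day 1 and day 14 from study participants". A third day applies to other measures: "Blood pressure and anthropometrics also will be assessed on days 1, 7, 14" (VI.A).
- **Minute of the oral glucose tolerance test (OGTT).** Section VI.D.4 has blood drawn "at each time point of the postprandial trial".
- **Period.** Section VI.D.3 calls the two periods Trial 1 and Trial 2.

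Day 1 comes before the diet: in the VI.D.3 timeline that visit covers "the collection of a fasting blood sample, and to pick-up daily meals". OGTT glucose (VI.C.2) and microbiota composition (VI.C.7) are measured on day 14 only. The primary comparison in VI.B.3 contrasts the WWB and WB endpoints between high and low responders. No period, sequence, baseline or diet-by-time term is named anywhere.

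**The concern.** In a 2x2 crossover with a pre-diet and a post-diet sample in each period, the diet term has no fixed meaning until the plan says how day 1 enters. If both days are outcomes and only main effects are fitted, the pre-diet samples count as if the assigned bread had already acted. Two analysts following the same sentence could then report WWB-versus-WB effects that differ twofold.

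The results at stake are the secondary group-mean comparisons. Section III says the study is not mainly designed for these, but it still expects a significant difference between the breads, lower endotoxin on WWB, and metabolome changes between the diets. This sentence is the only model offered for such claims.

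**Working it through.** **Inputs from the plan.** There are 40 participants and two periods. Blocks of four give 20 per sequence as randomised. Samples fall on days 1 and 14 (days 1, 7 and 14 for blood pressure and anthropometrics). There is no plan figure to reproduce: the only power statement concerns the responder comparison and is not tied to this model. All variances below are assumptions.

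**Step 1: what the diet term estimates.** Let δ be the WWB-minus-WB effect on day 14. The expected difference on day 1 is 0, assuming no carry-over past the washout. With balanced data, diet coded by arm and main effects only:

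diet coefficient = (day-1 difference + day-14 difference)/2 = (0 + δ)/2 = δ/2.

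No variance enters this result. A simulation with δ = 1.00 (800 runs; participant SD 1, participant-by-period SD 0.5, residual SD 0.5, period effect 0.5, day trend 0.3) agrees:

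- diet plus day: 0.504
- day 14 only, diet plus period: 1.004
- diet-by-day interaction, if that term were added: 0.998

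**Step 2: measures on days 1, 7 and 14.** If a share f of the effect is present by day 7, the main effect is (0 + f + 1)/3 of δ. That is 0.33 at f = 0 and 0.67 at f = 1.

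**Step 3: power.** Assume participant SD 1, residual SD 1, δ = 0.60 and no participant-by-period variance.

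- Diet plus study day: each participant's contrast is a difference of two two-value means, with variance 1/2 + 1/2 = 1. SE = √(1/40) = 0.158, and 0.30/0.158 = 1.90.
- Day 14, diet plus period: variance 1 + 1 = 2. SE = √(2/40) = 0.224, and 0.60/0.224 = 2.68.

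Averaging divides the SE by √2 but the effect by 2. Simulated power at a nominal 5%, with participant-by-period SD s and within-period correlation s²/(s² + 1):

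| s | Correlation | Diet + study day | Day 14: diet + period | Day 14: diet + period + day-1 value |
|---|---|---|---|---|
| 0 | 0 | 46% | 75% | 73% |
| 0.5 | 0.2 | 41% | 65% | 65% |
| 1 | 0.5 | 36% | 46% | 56% |

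The mean estimate is 0.30 in the first model and 0.60 in the other two. Only the top row is like for like. In the lower rows the first model's test exceeds its nominal 5% under these variances, which flatters its power. With the effect set at 0.6 day-14 SDs, diet plus period against the covariate model gives 74.3 v 74.0% at correlation 0.15, 74.3 v 74.7% at 0.2, 74.1 v 76.7% at 0.3 and 74.6 v 84.6% at 0.5.

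**Step 4: omitting period.** With n1 participants taking WWB first and n2 taking it second, the diet estimate shifts by −(period effect) × (n1 − n2)/(n1 + n2). For a period effect of 0.5:

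- 20/20: 0
- 24/16: −0.5 × 8/40 = −0.10
- 18/13: −0.5 × 5/31 = −0.08

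At 20/20 the estimate is unchanged, but under the Step 1 variances the mean model SE on day-14 data rises from 0.156 to 0.176.

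**The case against.** The strongest reply is that the model sentence comes shortly after the endpoint-versus-endpoint contrast in the same subsection. A competent analyst would then take day-14 values and read time as period, which is a standard crossover analysis. Halving needs one particular combination: both days as outcomes, diet coded by arm before any bread is eaten, and no interaction. A diet-by-day model would recover the full effect.

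This stands in part. The day-14 reading is open and sound, but the endpoint contrast is stated for the responder comparison and nothing links it to the mixed model. The day-1 samples are planned without any stated role. No interaction is named, so if time is study day, main effects only is the literal reading.

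Three further replies stand. Blocks of four keep the sequences near 20/20, so omitting period costs mainly precision; bias needs both unbalanced completers and a period effect. For anthropometrics there is little effect to dilute, since Section VI.C.5 adjusts energy intake to hold weight. The power figures rest on assumed variances and a nominal 5%, not on the Bonferroni or FDR thresholds the plan applies.

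A reader might also infer that tests from this model have a known inflated error rate. The documents do not support that: the departure from 5% can go either way, depending on variance components they do not give. Nor does treating time as OGTT minute describe the named glucose endpoint, which is already one AUC from 0 to 180 minutes.

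**Conclusion.** The point holds for the secondary day-1/day-14 measures. If time is study day and diet is coded by arm, the only model stated gives exactly half the day-14 effect, assuming balanced data and no carry-over. Under the simplest assumed variances, power is 46% against about 75% for day-14 values with diet and period. The factor of one half is algebra; the power figures are illustrations. Leaving out period also costs precision, and adds bias only with sequence imbalance and a real period effect.

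A reader might infer that the trial's main result is halved. It is not: the responder comparison uses endpoint differences, and glucose AUC and microbiota composition have no day-1 value to average in. A reader might also infer that responder labels need correcting for period; no calculation here supports that. The plan should be changed, but the primary comparison does not depend on it.

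**What to change.** Define time for each type of measure and state which coefficient is the diet effect.

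- **Day-1/day-14 measures:** day-14 value as outcome, diet and period fixed, participant random, preferably with that period's day-1 value as covariate. Report the diet coefficient as the effect.
- **Day-14-only measures (OGTT AUC, microbiota composition):** diet and period fixed, participant random, with one AUC per period for glucose.
- **Day 1/7/14 measures:** name the day-14 contrast as the effect.

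The cost is a few sentences and one or two degrees of freedom; every value needed is already in the planned schedule. The covariate takes one of those degrees of freedom. Under the assumed variances it gains power only when the within-period correlation exceeds about 0.2, and loses about two points (73 v 75%) when the correlation is zero. The documents give no value for it, so the covariate is a preference, whereas period and the day-14 outcome are the substance of the change.

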2. Recruitment. We will recruit participants through posted flyers, e-mail, electronic and newsprint advertisements (e.g. campus student and faculty/staff newspapers, local and regional newspapers; see attachment “*Advertisements*”), and word of mouth. The posted advertisements will instruct interested participants to call the study center ([name] Laboratory, Department of Human Sciences) or complete an online pre-screening survey to obtain further information. During the phone-in hours, a trained individual (i.e. project coordinator or graduate assistant) will be available to describe the study and determine preliminary qualification by conducting a scripted phone interview (e.g. do you take dietary supplements?, do you smoke?; see “*Phone Script*” attachment). The individual will record answers and assess whether the person calling is likely or not to be an acceptable study participant. If the caller and the interviewer agree that the caller should participate, the prospective participant will be invited to a screening meeting, where the study will be fully described, and the individual will be provided a consent form to complete prior to any involvement in the study procedures. Data collected during this phase will include participant’s age, health status, physical activity, and contact information (see “*Informed Consent*” attachment).

3. Power Calculation and Data Analysis. [name] (biostatistician; *co-PI and Dept of Biomedical Informatics*) performed a power analysis. To ensure that the order by which each participant completes each trial is randomized, a random sequence generator (<http://www.random.org/sequences/>) will be used to determine the order by which each participant will undergo the two trials. We will primarily compare the

within-subject changes (WWB endpoint vs. WB endpoint) between high-responders and low-responders. We anticipate to have 6-12 high-responders and 5-10 low-responders of the total 40 study participants to achieve 80% power to detect a 1.6-fold difference in the changes of postprandial glucose levels (AUC from 0 to 180 minutes) between high-responders and low-responders, at the expected coefficient of variation (CV) 0.5 at a significant level of 0.05.

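### The Bonferroni family for non-omics measures is undefined, so the significance level of the glucose AUC is open; Holm would serve that family better at no cost

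*Combined protocol and SAP*

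**What the plan says.** All the relevant text is in Section VI.B.3 (Power Calculation and Data Analysis).

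- The main comparison concerns "within-subject changes (WWB endpoint vs. WB endpoint) between high-responders and low-responders".
- The power statement is "80% power to detect a 1.6-fold difference in the changes of postprandial glucose levels (AUC from 0 to 180 minutes"), "at the expected coefficient of variation (CV) 0.5 at a significant level of 0.05". On group sizes it says "We anticipate to have 6-12 high-responders and 5-10 low-responders of the total 40 study participants". No adjustment for multiple testing is mentioned there.
- Two multiplicity rules follow. The first is "False discovery rate (FDR) will be used to control type I error rate for microbiome and metabolome data". The second is that "the Bonferroni method will be applied for other measures (e.g., inflammatory markers").

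The protocol does not list the measures under the second rule, give the number of tests, say whether Bonferroni runs across all measures or within domains, or say whether the powered AUC is inside or outside it.

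**The concern.** The second rule is defined by contrast with the omics data. Glucose AUC is neither microbiome nor metabolome data, so on the plain wording it falls under Bonferroni, while the power statement treats it as a single test at 0.05. The two statements agree only if the AUC is exempt, and the protocol does not say that it is.

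At stake is how the main result is read. A p-value of 0.01 would be a success if the AUC is exempt and a failure if it is one of some 28 tests. With nothing documented, that choice could be made after the data are seen. A smaller point is that plain Bonferroni gives up some power on the secondary outcomes that Holm recovers without weakening error control.

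**Working it through.** **Inputs from Section VI.B.3.** A 1.6-fold difference, CV 0.5, level 0.05, power 80%, 6-12 high-responders and 5-10 low-responders. Not stated, and assumed here: a two-sided test, and the scale of the CV. On the raw scale d = (1.6 - 1)/0.5 = 1.2. On the log scale d = ln 1.6 / sqrt(ln 1.25) = 0.470/0.472 = 0.995.

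**Step 1: reproduce the stated 80%.** Normal approximation: power = Φ(d·sqrt(n1·n2/(n1+n2)) - z(1-α/2)).

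- For 12 v 10 with d = 1.2: 1.2 × sqrt(120/22) = 2.803, and Φ(2.803 - 1.960) = 80.0%.
- The t test (noncentral t) gives 76.0% on the same inputs. On the log scale the t test gives 59.9%.
- The 80% is reached only at the top of the stated group sizes. At 6 v 5 the same raw-scale inputs give 51% (normal) or 42.5% (t test).

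**Step 2: count the non-omics measures.** Each is counted once:

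| Group | Source | Count |
|---|---|---|
| Systolic and diastolic pressure, BMI (assumed split) | VI.A, VI.C.1 | 3 |
| Fasting glucose, total cholesterol, HDL-C, triglyceride | VI.C.2 | 4 |
| Fasting insulin; HOMA-IR | VI.C.2; IV | 2 |
| Glucose AUC | VI.B.3, VI.C.2 | 1 |
| Fecal calprotectin and myeloperoxidase | VI.C.2 | 2 |
| Serum inflammatory markers | VI.C.2 | 5 |
| Blood-cell gene expression | VI.C.2 | 8 |
| Serum endotoxin | VI.C.3 | 1 |
| Two permeability ratios | VI.C.6 | 2 |
| **Total** | | **28** |

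The total is 33 if the five serum markers are counted both fasting and postprandial. Then 0.05/28 = 0.0018 and 0.05/33 = 0.0015.

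**Step 3: power for 12 v 10 at 1.6-fold, by size of the family (m) that contains the AUC.**

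| m | α = 0.05/m | Normal, d = 1.2 | t test, d = 1.2 | t test, log scale |
|---|---|---|---|---|
| 1 (AUC exempt) | 0.05 | 80.0% | 76.0% | 59.9% |
| 2 | 0.025 | 71.3% | 64.9% | 47.5% |
| 5 | 0.01 | 59.0% | 49.8% | 32.9% |
| 28 | 0.0018 | 37.4% | 25.7% | 14.2% |
| 33 | 0.0015 | 35.6% | 23.8% | 13.0% |

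For example, at m = 28: Φ(2.803 - 3.124) = 37.4%.

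**Step 4: Holm against Bonferroni.** Holm compares the smallest p-value with 0.05/m, the next with 0.05/(m-1), and so on until one fails. Its first threshold equals Bonferroni's and the later ones are looser, so it rejects everything Bonferroni rejects. Its family-wise error stays at or below 0.05 under any dependence. Simulation with 25 measures, correlation 0.3 and 40 paired observations, with assumed standardized effects of 0.6 (3 or 10 affected) and 0.7 (15 affected), gave these per-test powers:

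| Measures truly affected | Bonferroni | Holm | Gain (points) |
|---|---|---|---|
| 3 of 25 | 68.1% | 68.7% | 0.6 |
| 10 of 25 | 68.1% | 71.3% | 3.2 |
| 15 of 25 | 86.1% | 90.3% | 4.2 |

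**The case against.** The strongest reply is that the AUC was never meant to be in the family. Section VI.B.3 first says which comparison is made primarily and attaches 0.05 to the AUC. Only later does it turn to other measures, with inflammatory markers as the example. An author writing in that order may well mean measures other than the powered one. This reading is fair, and under it the AUC loses no power.

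For that reason the documents do not support a stronger claim that a reader might infer, namely that the AUC will be tested at about 0.002 with well under half the planned power. No section gives 0.002, a number of tests, or a single family of all non-omics measures. The count of 28 is mine. It includes HOMA-IR, which appears only in Section IV as a fallback for defining response, and BMI, although Section III expects body mass not to change. Dropping both gives 0.05/26 = 0.0019, so the count is discretionary but not delicate. On the calculation that reproduces the plan's 80%, the large-family figure of 36-37% is just under half of 80%; the much lower figures need a t test or a log scale that the plan does not state.

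It is also true that Bonferroni is valid and that Holm's gain is modest, under 1 point when few measures respond. That limits the benefit but is no reason to keep Bonferroni, since the change has no downside.

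What remains is that the text allows all of these readings and does not choose among them.

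**Conclusion.** The point holds as an undefined family with a possible conflict of significance levels; it does not show that the AUC will be under-tested. The admissible readings put the AUC's level anywhere from 0.05 down to about 0.0015. Raw-scale power for 12 v 10 on the normal approximation then runs from the stated 80% (exempt), through 59-71% (2 to 5 tests per domain; 50-65% by t test), to 36-37% (28 to 33 tests; 24-26% by t test, 13-14% by t test on the log scale). These figures rest on two-sided testing, the top of the stated group sizes, the assumed CV scale, and my own count of measures.

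The Holm part stands whatever the family turns out to be: the same family-wise error, never fewer rejections, and about 1 to 4 points of per-test power in the scenarios simulated.

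One limit applies to every power figure here. Sections II.D and III describe responders by improved glucose metabolism or a fall in postprandial glucose. Whether groups defined by glycemic response can be validly compared on that same response is a separate issue, which fixing the significance level does not settle.

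**What to change.** Amend Section VI.B.3 before analysis, in about two sentences:

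- State that one glucose AUC (0-180 min) contrast is the single primary test, at two-sided 0.05, outside the multiplicity family. Name the contrast explicitly: the high- v low-responder comparison that the power statement uses, or WWB v WB in all participants. If the latter is chosen, the power statement has to be redone for it.
- List the remaining non-omics outcomes (clinical, inflammatory, endotoxin and permeability) as one secondary family, say whether fasting and postprandial values count separately, and control the family at 5% with Holm in place of Bonferroni.

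The 5% then applies to the primary test and to the secondary family separately, and the text should say so. FDR for the omics data is unchanged. The change needs no further data, participants or staff, and the secondary family keeps its error control. Holm is available in both R and SAS, the packages that the plan names.
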